#### Study Participants

Potential subjects participated in informed consent procedures approved by Institutional Review Boards for each performance site and the Department of Defense Human Research Protection Office (HRPO). A Data Safety Monitoring Board (DSMB) oversaw safety and progress of the study. To be included in the trial, veteran or civilian women and men, aged 18-70 years were required to meet past-month criteria for posttraumatic stress disorder (PTSD) according to DSM-5. Participants were required to have a CAPS-5 score of  $\geq$  25 at screening in order to enter the trial.

Exclusion criteria were: 1) current, imminent risk of suicide (as assessed by the C-SSRS (23)), 2) active psychosis, 3) moderate or severe DSM-5 alcohol or other substance use disorder in the past 3 months, 4) unable to attend regular appointments, 5) prior intolerance of or allergy to losartan or other ARBs, 6) medical illness likely to result in imminent hospitalization or for which treatments are contraindicated (based on lab results, medical history and physical exam) (e.g., systolic blood pressure < 90 mm Hg), 7) serious cognitive impairment (as evidenced by cognitive impairment felt likely to interfere with the ability to participate meaningfully in the study); traumatic brain injury was not excluded unless there was serious cognitive impairment, 8) concurrent ACE Inhibitors or ARBs, 9) concurrent antidepressants or antipsychotics, and 10) currently pregnant or trying to become pregnant, or of childbearing potential and unwilling to use a proven method of birth control. Potential participants were required to be off of all antidepressants for a minimum of 2 weeks (6 weeks for fluoxetine) prior to randomization; only 2 participants had been on SSRIs prior to entering the study. Sleep agents (e.g., trazodone < 200 mg; eszopiclone; zolpidem) were allowed as long as the dose had been stable for at least 2 weeks; 14 patients used p.r.n. sleep aids during the study. Participation in a trauma-focused psychotherapy during the trial was prohibited. Participation in other psychotherapeutic modalities maintained for 3 months before and during the trial was permitted; 2 patients were on long-term supportive therapy during the study.

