#### Study Procedures

All intakes and interview measures were completed by trained study personnel qualified to conduct the intake assessment. CAPS-5 training and certification was conducted (by [name] PhD) at the start of the study and yearly recalibration assessment reviews took place at each site. At intake, a standardized past and current medical history with review of symptoms (including allergies to losartan, other ARBs, or any other medications) was obtained. The study physician also conducted a screening medical examination that included determination of standing and sitting blood pressure. Blood was drawn for renal and liver function tests, urine for drug screen, and a baseline EKG. If the patient was a woman of childbearing potential a urine pregnancy test was also done.

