#### Study Assessments

Study assessments occured at baseline week (week 0) and weeks 1, 2, 4, 6, 8 and 10. These assessments included interview and self report measures of symptoms and function, as well as evaluation of adverse events and assessment of standing and sitting blood pressure. The primary endpoint was at 10 weeks and the primary outcome measure was the Clinician Administered PTSD Scale for DSM-5 (CAPS-5; (24)), the gold standard in PTSD assessment. The CAPS-5 past-month was administered at intake and the past-week version re-administered at Weeks 0 (baseline), 4, 8 and 10 week endpoint (or earlier endpoint if the subject discontinued early from the study). Key secondary measures were the PTSD Checklist for DSM-5 (PCL-5; (25)) and the Clinical Global Impressions of Improvement Scale (CGI-I; (26)), and the Patient Health Questionnaire-9 (PHQ-9; (27)) for depressive symptoms.

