## STATISTICAL ANALYSIS PLAN

### Statistical Methods

The primary outcome (CAPS-5) was analyzed using an MMRM (mixed model repeated measures) approach based on a modified intent-to-treat (mITT) population, defined as randomized subjects who initiated treatment and had both a baseline and at least one postbaseline outcome score during the blinded phase of the study (Week 10). Participants from the mITT population who were included in the MMRM model also required both a baseline and at least one post-baseline CAPS-5 score. The model included as the dependent variable change from baseline in CAPS-5 total score at each post-baseline visit (Weeks 4, 8 and 10). Independent variables in the MMRM model included treatment, visit, treatment-by-visit interaction, and baseline CAPS-5 total. Visit was treated as a categorical variable. Unstructured variance-covariance structure was used. This same analysis was also repeated on the per protocol population, defined as as all eligible subjects for whom the 10-week assessments for the primary analysis were available and who were dispensed at least 50mg of the protocol prescribed medication at the 6-week time point. Descriptive analyses were performed to compare baseline data between treatment groups. Categorical variables were evaluated using Fisher's exact test. Continuous variables were analyzed with Wilcoxon's rank sum test. Safety data were summarized overall and by treatment groups for the blinded and extended phases of the study. Fisher's exact test was used to compare the number of subjects between groups who experienced any adverse events.

The study was a priori powered assuming 10% attrition and an alpha set to 0.05 using a twosided, two-sample t-test. Based on a sample size of 160 subjects to have an evaluable sample size of 144 (72 per arm), we could detect with 80% power a standardized change score between the groups of 47%. All analyses are based on the modified intent-to-treat (mITT) sample unless otherwise specified.

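### The only inferential safety comparison, any adverse event by Fisher's test, is poorly sensitive to a pressure-related excess, and no between-arm blood-pressure estimate is specified although pressure is measured at every visit

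*Combined protocol and SAP*

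**What the plan says.** Study Assessments places "evaluation of adverse events and assessment of standing and sitting blood pressure" among the visit procedures, and the schedule reads "Study assessments occured at baseline week (week 0) and weeks 1, 2, 4, 6, 8 and 10". Study Procedures adds an earlier reading, in a "screening medical examination that included determination of standing and sitting blood pressure". Study Participants gives low pressure as its example of an excluding medical condition ("e.g., systolic blood pressure < 90 mm Hg").

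Statistical Methods has two sentences on safety analysis. The first is descriptive: "Safety data were summarized overall and by treatment groups for the blinded and extended phases of the study". The second is inferential, a Fisher's exact test to "compare the number of subjects between groups who experienced any adverse events". Blood pressure is not mentioned anywhere in the SAP text.

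The SAP extends the primary model to the other continuous secondary outcomes. Blood pressure is not stated to be one of these: the list that opens "Key secondary measures were the PTSD Checklist for DSM-5" continues with the CGI-I and the PHQ-9 only. The default analysis set for everything is the mITT set, which requires a post-baseline outcome score. No separate safety set is defined.

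**The concern.** An any-event endpoint scores each subject once. A subject who already has a headache or a cold cannot add to the difference between arms by also becoming dizzy on standing. A drug-specific excess therefore shrinks as background events become more common. A fall in pressure that nobody records as an adverse event does not enter the test at all.

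The trial collects the measurement that would answer the question directly, but the plan commits to no estimate from it. A non-significant any-event result could then be read as reassurance about blood pressure, which it would not be.

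The default analysis set adds a smaller problem. A treated subject who leaves before giving any post-baseline outcome score falls outside the mITT set, and so outside the safety comparison as written. Someone who stops very early for poor tolerability could be such a subject.

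**Working it through.** **Inputs from the documents.** 160 randomised 1:1, 10% attrition, 144 evaluable (72 per arm), two-sided alpha 0.05, 80% power for a standardised difference of 0.47.

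**The plan's own figure.** 160 × 0.9 = 144. The noncentrality is 0.47 × √(72/2) = 2.82 and the critical t on 142 df is 1.977. Power is 0.7998, so the stated 80% reproduces. This figure concerns efficacy; the documents give none for safety.

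**Assumptions.** The documents give no adverse-event rates and no blood-pressure SD. Let b be the proportion of controls with any event, and e the proportion of subjects in whom the drug adds a specific event, independently of other events. Then

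- treated any-event rate = b + (1 − b)e, so the any-event difference is (1 − b)e;
- direct comparison with a 3% control rate: 0.03 + 0.97e, which is 12.7% for e = 10% and 17.55% for e = 15%.

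**Exact power of the two-sided Fisher test, 72 per arm (full enumeration).**

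| Comparison | Control | Treated, e = 10% (15%) | Power, e = 10% (15%) |
|---|---|---|---|
| Any event, b = 10% | 10% | 19% (23.5%) | 26% (52%) |
| Any event, b = 20% | 20% | 28% (32%) | 15% (31%) |
| Any event, b = 30% | 30% | 37% (40.5%) | 11% (21%) |
| Any event, b = 60% | 60% | 64% (66%) | 5.5% (8.4%) |
| Specific event directly | 3% | 12.7% (17.55%) | 47% (79%) |

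With no drug effect and b = 60%, the test rejects 3.4% of the time, so 5.5% is close to its null rejection rate.

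**Without independence.** If the added events fell only in subjects with no other event, the comparison at b = 60% would be 60% v 70% (75%), with power 19% (42%).

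**The same contrast as estimates** (e = 10%, Wald 95% intervals).

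- Any event, 60% v 64%: SE = √(0.60×0.40/72 + 0.64×0.36/72) = 0.0808. The difference is 4.0 points, ±15.8.
- Specific event, 3% v 12.7%: SE = √(0.03×0.97/72 + 0.127×0.873/72) = 0.0441. The difference is 9.7 points, ±8.6.

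**Mean pressure at one visit.** The 95% half-width is 1.977 × SD × √(2/72): 2.6, 3.3, 4.0 and 4.9 mm Hg for assumed SDs of 8, 10, 12 and 15. A true difference of 5 mm Hg would have power 96%, 85%, 70% and 51% respectively.

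**The case against.** The strongest reply is that the plan is not silent. It summarises safety data by arm, and blood pressure sits beside adverse events in the visit schedule, so a natural reading is that it is among the data summarised. Hypotension, dizziness and syncope reported as adverse events all count in the any-event total. The trial was powered for efficacy only, and by-arm summaries with one overall test are a common and defensible safety plan. The power figures rest on assumed rates, and a low background rate weakens the contrast. The direct comparison itself has only 47% power for e = 10%.

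Much of this stands, and it rules out three stronger readings that a reader might infer.

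- That the any-event test cannot detect a pressure harm. It can, with low sensitivity; only changes never recorded as events escape it.
- That the pressure readings are never compared between arms. The planned summaries may show them by arm; the text does not say.
- That a specific excess is always diluted almost to nothing. That needs common background events and roughly independent event types. At a 10% background, power is 26% (52%).

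Nor do the documents make low pressure a declared safety endpoint: it appears only as an example within an exclusion criterion.

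What the reply does not remove is that an unspecified summary commits nobody to a variable, a contrast or an interval. The point also does not depend on power as the criterion. Under the assumptions shown at a 60% background, the any-event estimate is both smaller and less precise than the direct one.

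**Conclusion.** The concern holds in a limited form. The one inferential safety comparison is poorly sensitive to a specific excess of pressure-related events, and the plan names no between-arm blood-pressure estimate although it schedules the readings at every study visit.

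Under independence, any-event power runs from 26% (52%) at a 10% background down to 5.5% (8.4%) at 60%, against 47% (79%) for the direct comparison. The direct comparison does better in every scenario in the table, but the size of the gap depends on the background rate, the 3% control rate and the overlap between event types, none of which the documents give.

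The analysis-set problem follows from the text: mITT is the default and no exception is made for safety. How many treated subjects it would exclude cannot be determined from the documents. The primary efficacy conclusion is not affected.

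**What to change.** Keep the any-event count and its test, and add the following for the blinded phase.

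1. Fit the MMRM already specified for the primary outcome to change from baseline in sitting systolic pressure, and separately to change in the standing-minus-sitting difference. Report the between-arm difference with 95% CI at Weeks 1, 2, 4, 6, 8 and 10. With six post-baseline visits an unstructured covariance has 6 × 7/2 = 21 parameters, against 3 × 4/2 = 6 for the CAPS-5, so name a fallback structure in case the model does not converge.
2. List the adverse-event terms that count as pressure-related (for example hypotension, dizziness, syncope). Report the number of subjects with at least one such event per arm, with risk difference and 95% CI.
3. Define a safety set of all treated subjects and use it here instead of the mITT default. The models will still need a baseline and at least one post-baseline pressure reading; the event counts will not.
4. Label all of this as safety estimates without multiplicity control. The document describes the trial as already conducted, so analyses added now should also be described as added afterwards.

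The cost is a few model runs and one table from data already scheduled for collection. The drawback is several uncontrolled estimates, some of which may differ by chance. No dose, visit or clinical rule changes.

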Analogous methods to the primary analysis were used for the other continuous secondary outcomes. The categorical secondary outcome, treatment response status, (response defined as a score of 1 ["Much Improved"] or 2 ["Improved"] on the CGI-I) was analyzed using a generalized estimating equation (GEE) model for binary data. The model included the binary responder status at Weeks 1, 2, 4, 6, 8 and 10 as the dependent variable; treatment, visit and the treatment-by-visit interaction as independent variables. Statistical analyses were performed using R version 3.5.2 (http://www.r-project.org).

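### The mITT default covers the safety analyses too, so a treated participant without a post-baseline outcome score is outside the adverse-event denominator as written

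*Combined protocol and SAP*

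**What the plan says.** All of the population rules are in Statistical Methods of the combined protocol and SAP.

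- The default: "All analyses are based on the modified intent-to-treat (mITT) sample unless otherwise specified".
- The mITT set: "randomized subjects who initiated treatment and had both a baseline and at least one postbaseline outcome score", with the score falling in the blinded phase.
- The safety summary: "Safety data were summarized overall and by treatment groups for the blinded and extended phases of the study".
- The safety test: Fisher's "exact test was used to compare the number of subjects between groups who experienced any adverse events".

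The only other set defined is per protocol. It is narrower than mITT and is used to repeat the primary analysis. No safety, as-treated or all-treated set is defined anywhere.

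Two statements in Study Assessments bear on who could be affected. Adverse events are collected at the same visits as the scores: "These assessments included interview and self report measures of symptoms and function, as well as evaluation of adverse events". A CAPS-5 is also planned at Week 10 "or earlier endpoint if the subject discontinued early from the study".

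**The concern.** A safety denominator should normally count everyone exposed to study drug. Here the written rule adds a condition met only after randomization: having at least one efficacy score. Someone who starts treatment and leaves before giving a score is exposed but not counted. Study Design provides a tolerability route to early exit, since participants who could not tolerate the starting dose were withdrawn. An early leaver of that kind matters for safety.

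At stake are the adverse-event rates by arm and the comparison between them. Leaving out exposed participants with no recorded event raises that arm's rate. Leaving out participants with a known event lowers it. A reader of the safety tables also cannot tell from the plan which denominator applies.

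**Working it through.** **1. Does the text lead to this result?**
- The default covers every analysis for which nothing else is specified.
- The safety summary and the adverse-event test specify no population. The word overall in the summary sentence is set against by-arm reporting; it means arms pooled and does not define a set.
- Where the plan departs from plain mITT it says so: it names the per protocol set, and it adds a CAPS-5 condition for the MMRM.
- So safety falls under mITT, and mITT excludes a treated participant with no post-baseline outcome score.

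**2. How large could the group be?**
- The separate CAPS-5 condition for the MMRM shows that the mITT condition is wider: any outcome score qualifies.
- Scores are due from Week 1. For CGI-I response, "The model included the binary responder status at Weeks 1, 2, 4, 6, 8 and 10 as the dependent variable".
- A CAPS-5 is planned at early discontinuation.
- What remains is mainly a participant who started treatment, left before Week 1 and had no endpoint assessment. Because adverse events are evaluated at the same visits, most such participants would have no scheduled adverse-event record. Any known event would have come to light outside a scored visit.

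**3. The plan's own figures, which are not in dispute.** For a standardized difference of 0.47, two-sided alpha 0.05 and 80% power, n per arm = 2 × (1.960 + 0.842)² / 0.47² = 71.1, rounded up to 72. Exact t-test power at 72 per arm is 80.0%. Allowing for 10% attrition, 144 / 0.90 = 160. These reproduce, and nothing in this point changes them.

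**4. The safety denominator.** Assume all 160 planned participants started treatment, and let k be the number with no post-baseline score. The documents do not give k. The mITT denominator is 160 − k:

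| k | Denominator |
|---|---|
| 0 | 160 |
| 4 | 156 |
| 8 | 152 |
| 16 | 144 |

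The last row is the extreme in which all of the assumed 10% attrition occurs before any score.

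**5. Shift in one arm's rate.** Assume n = 80 treated in the arm, x with any adverse event, and k = 2 excluded.
- Neither excluded participant has a recorded event: the rate rises by x/(n − k) − x/n = kx / [n(n − k)]. This is largest at x = n − k = 78: 78/80 = 97.5% becomes 78/78 = 100%, a rise of 2.5 points.
- Both have an event: the rate falls by k(n − x) / [n(n − k)]. This is largest at x = k = 2: 2/80 = 2.5% becomes 0/78 = 0%, a fall of 2.5 points.
- The bound is therefore k/n = 2/80 = 2.5 points. Less extreme assumed rates give smaller shifts:

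| Assumed events, all treated | Neither excluded had an event | Both excluded had an event |
|---|---|---|
| 60/80 (75.0%) | 60/78 (76.9%), +1.9 | 58/78 (74.4%), −0.6 |
| 24/80 (30.0%) | 24/78 (30.8%), +0.8 | 22/78 (28.2%), −1.8 |

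**The case against.** The strongest reply is that the affected group may not exist. The mITT condition is "at least one postbaseline outcome score during the blinded phase of the study", which any instrument can satisfy from Week 1, and a participant withdrawn for intolerance would still be due the early-endpoint CAPS-5. This stands as a limit on size. It does not make the group empty, because a planned endpoint assessment can be missed.

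A second reply concerns intent. The default sentence closes the sample-size paragraph, not the safety text, and safety is also summarized for the extended phase whereas mITT is defined on the blinded phase. A separate safety set may have been meant. But mITT members can be followed into a later phase, so the mention of that phase names no population, and the sentence as written covers all analyses.

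Two stronger readings are tempting, and the documents support neither.
- A reader might infer that the safety tables were in fact run on mITT, or that harms were under-counted. The documents do not show which denominator was used, how many participants were left out, or in which arm. Since most affected participants would have no scheduled adverse-event record, leaving them out could as well raise a rate as lower it.
- A reader might infer that the adverse-event comparison could change from non-significant to significant. With invented counts it can: 60/80 v 48/80 gives Fisher p = 0.063, and 60/78 v 48/80 gives p = 0.027. Those counts were chosen to lie near 0.05, a threshold the plan sets for the power calculation and not for this test. From 52/80 v 48/80 (p = 0.62), excluding two from one arm, with both or neither having had an event, leaves p between 0.41 and 0.74. No decision rule in the plan depends on this test.

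**Conclusion.** The point holds as a reading of the text: as written, safety is analyzed on mITT, and a treated participant without a post-baseline outcome score is not counted. It is minor. The group is probably small and possibly empty. Under the assumption of 80 treated in an arm and two excluded, the arm's adverse-event rate moves by at most 2.5 percentage points, and the direction cannot be known from the documents. If no treated participant lacks a score, nothing changes. The point shows an unsuitable rule in the plan; it does not show an error in any reported safety result.

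**What to change.** Replace the default sentence with wording such as: *Efficacy analyses use the mITT sample by default. The safety summaries and the adverse-event test include every randomized participant who initiated treatment, whether or not an outcome score exists.* This keeps the plan's existing criterion of treatment initiation and introduces no new one.

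State which denominator the safety tables used. Report by arm how many treated participants mITT excludes, and how many of those had no adverse-event assessment after baseline.

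The second count is needed because the change has a small downside. Participants with no contact after baseline have unknown adverse-event status, and counting them as having no event can slightly dilute that arm's rate. In the assumed example, adding two such participants takes 60/78 (76.9%) to 60/80 (75.0%).

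The cost is a revised sentence or two and two counts per arm. The safety tables need rerunning only if they used mITT and the excluded count is not zero. No extra patients, visits or staff are needed.

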#### STUDY PROTOCOL

#### Study Design

The trial was conducted between 01AUG 2016 and 25FEB 2020 at 6 clinical sites: five University academic medical sites and one University active-duty military hospital. The trial consisted of ten-week, randomized, double-blind, placebo-controlled administration of losartan or placebo. Eligible participants were randomized in a 1:1 ratio based on a randomly permuted block design stratified by site. Participants were prescribed 25 mg of active drug or placebo at Week 0 and then flexibly uptitrated (as tolerated) to 50 mg by Week 2, 75 mg by Week 4, and then 100 mg at Week 6. If significant side effects were encountered, the dosage could be held or reduced to a minimum of 25 mg and held stable at Week 6. Participants unable to tolerate the 25 mg dose were withdrawn from the study.

Losartan and placebo were prescribed as identical capsules, with the losartan overencapsulated. Randomization lists were prepared by the biostatistics analytical team (led by SJ) and distributed to research pharmacies at the sites who dispensed the drug. Only the biostatistics team had access to the treatment assignment codes.

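### The GEE for CGI-I response states no handling of missing visits and no working correlation, so as written it rests on a stricter withdrawal assumption than the primary MMRM

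*Combined protocol and SAP*

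**What the plan says.** In the SAP, Statistical Methods, the categorical secondary outcome is CGI-I responder status. It "was analyzed using a generalized estimating equation (GEE) model for binary data. The model included the binary responder status at Weeks 1, 2, 4", continuing through Weeks 6, 8 and 10. The only model terms are arm, visit and their interaction; baseline severity is not included. The sentence that carries the primary method over to other outcomes applies to continuous secondary outcomes only, so it does not supply a missing-data rule here.

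For the primary outcome the same section says: "The primary outcome (CAPS-5) was analyzed using an MMRM (mixed model repeated measures) approach". That model has an unstructured covariance and adjusts for baseline CAPS-5. The mITT population needs a baseline score and only one later score, so it can include people with no Week 10 CGI-I.

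Missing Week 10 data are expected: "The study was a priori powered assuming 10% attrition". The protocol's Study Design section adds one route out of the trial: "Participants unable to tolerate the 25 mg dose were withdrawn from the study". Study Assessments lists CGI-I response among the key secondary measures. It attaches an early-endpoint assessment ("or earlier endpoint if the subject discontinued early from the study") to CAPS-5 and states none for CGI-I.

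**The concern.** An ordinary GEE solves estimating equations over the visits it is given. Without weights or imputation, it is in general consistent only when being observed is unrelated to response given the model's covariates, which here are arm and visit. The MMRM is a likelihood method and also allows withdrawal to depend on observed CAPS-5 scores. The two analyses may therefore treat the same withdrawals under different assumptions, and the plan neither says so nor tests it.

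If people who are not improving leave, the observed response rate is too high. If this happens more in one arm, part of the error passes into the treatment difference on a key secondary measure. CGI-I and CAPS-5 could then appear to disagree, or to agree, partly because of how withdrawal was handled.

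**Working it through.** **The plan's own figures.** 160 × (1 − 0.10) = 144, or 72 per arm. The detectable standardized difference at 80% power and two-sided alpha 0.05 is (1.960 + 0.842) × √(2/72) = 0.467 by the normal formula and 0.470 by the noncentral t. Power at 0.47 is 0.800 by the noncentral t. The stated design reproduces and is not in dispute. The documents give no CGI-I response rate, no dropout by arm and no power for CGI-I, so the inputs below are assumptions, except that 10% dropout matches the planned attrition.

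**What the GEE estimates under independence.** The mean model has one free parameter per arm and visit. The estimating equation for each cell is Σ(Y − μ) = 0 over observed participants, so the estimate is the observed proportion. With true rate p and probabilities a and b of being observed for responders and non-responders:

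bias = p(1 − p)(a − b) / [pa + (1 − p)b]

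If withdrawal depends only on arm and visit, a = b and the bias is zero.

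**Extreme case.** Take p = 0.40 in both arms, dropout of 20% versus 10%, and every withdrawn participant a non-responder. The observed rates are 0.40/0.80 = 50.0% and 0.40/0.90 = 44.4%, a spurious 5.6 points. This is an outer limit for those dropout rates, not an expectation.

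**Per-arm bias.** A simulation of one arm used 200,000 subjects, six binary visits, a Week 10 rate of about 0.50 and a latent AR(1) correlation of 0.7. Dropout depended only on the last observed response. The odds ratio compares non-responders with responders for leaving at the next visit.

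| Dropout by Week 10 | Odds ratio | Full-data rate | Independence | Exchangeable | Unstructured |
|---|---|---|---|---|---|
| 10% | 1 | 0.501 | 0.501 | 0.501 | 0.501 |
| 10% | 3 | 0.500 | 0.504 | 0.498 | 0.499 |
| 10% | 10 | 0.502 | 0.510 | 0.500 | 0.502 |
| 20% | 3 | 0.500 | 0.510 | 0.497 | 0.500 |
| 20% | 10 | 0.500 | 0.515 | 0.496 | 0.499 |
| 30% | 3 | 0.501 | 0.517 | 0.496 | 0.499 |
| 30% | 10 | 0.500 | 0.526 | 0.492 | 0.497 |

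Under independence the bias is 0.4 to 0.8 points at 10% dropout, 1.0 to 1.5 at 20% and 1.6 to 2.6 at 30%. Exchangeable correlation errs by at most 0.8 points in the other direction, and unstructured by at most 0.3.

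**Treatment difference.** A two-arm simulation used 400,000 per arm, 45% response in both arms, no true difference, and dropout driven by last responder status:

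- 13% dropout in both arms: difference unbiased.
- 21% versus 8%: +1.6 points for the arm with more dropout.
- 27% versus 8%: +2.7 points for that arm.
- Inverse-probability weighting brought the bias back to about zero.

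In a GEE fit of the 27%/8% case with 6,000 per arm, the full-data difference was −0.009. Independence gave +0.021, a shift of 0.030. Exchangeable gave −0.006, a shift of 0.003.

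**Scale.** At 72 per arm and 45% response, the standard error of the difference is √(2 × 0.45 × 0.55/72) = 0.083. The simulated biases are 1.6/8.3 = 0.2 and 2.7/8.3 = 0.3 of one standard error.

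**The case against.** The strongest reply is that the working correlation nearly settles the matter. In the 27%/8% case, exchangeable correlation removed about 1 − 0.003/0.030 = 90% of the shift. This stands, and it limits the point. A reader might infer that withdrawn participants vanish from the Week 10 rate. That is exact only under independence, which the SAP does not name, and even then their earlier visits remain in the model. Nor does the SAP say that only observed visits are used; that reading comes from its silence. Yet the silence leaves the choice that governs the bias open, and a non-independence structure still does not guarantee validity under MAR.

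A second reply is that the withdrawal rule is narrow. Study Design lets the dose be held or lowered for side effects, and only people who cannot tolerate the lowest dose are withdrawn. If leaving depends on arm and visit but not on response, the GEE is sound. This also stands. A reader might infer that the bias favours losartan, but the documents give neither dropout by arm nor a link between intolerance and response, so no direction can be claimed.

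Third, different assumptions for a continuous and a binary outcome are not in themselves a contradiction, and the primary analysis is untouched. Both are correct. What remains is a key secondary endpoint with an avoidably stricter assumption.

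**Conclusion.** The point holds as an inexpensive improvement to a secondary analysis. If the GEE is fitted to observed visits, it needs withdrawal to be unrelated to response given arm and visit, which is more than the MMRM needs.

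The size is modest: under about 1 point per arm at 10% dropout, near zero in the difference when dropout is the same in both arms, and about 2 to 3 points when it is strongly unequal and related to response. These figures apply to an independence working correlation and rest on assumed response rates, visit correlations and dropout patterns. The plan's 10% attrition is a single overall figure for evaluability, and the larger, unequal rates used above have no source in the documents.

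The documents do not support a claim that the CGI-I result is materially wrong or biased in a known direction. They also do not show that CGI-I went unrecorded at early termination; they state an early-endpoint assessment only for CAPS-5.

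**What to change.** In the SAP's paragraph on the categorical secondary outcome:

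1. Multiply impute missing CGI-I separately by arm, from baseline CAPS-5 and all observed CGI-I, CAPS-5 and PCL-5 scores. Fit the same GEE to each completed data set and combine the results by Rubin's rules. Alternatively, weight each visit by the inverse estimated probability of still being observed, given arm, previous CGI-I and previous CAPS-5 or PCL-5.
2. State the working correlation. Once imputation has filled every visit, the arm-by-visit rates no longer depend on it; without imputation or weighting, they do.
3. Optionally, add an analysis counting withdrawn participants as non-responders. It is a different assumption, not a correction. With assumed observed rates of 0.60 and 0.40 for losartan and placebo, the difference of 0.20 becomes 0.60 × 0.85 − 0.40 × 0.95 = 0.13 if dropout is 15% and 5%, and 0.60 × 0.95 − 0.40 × 0.85 = 0.23 if it is 5% and 15%.

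The cost is a few lines of text, modest programming on data already collected, and a slightly wider interval. Imputation and weighting still assume MAR and do not protect against withdrawal that depends on unobserved response. Adding a CGI-I rating at early-endpoint visits is not available, because Study Design dates the end of the trial to February 2020. If the planned GEE has already been run, label the imputed or weighted analysis as added afterwards.
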